	
will run over two phases.
 
Part 1 – Treatment Phase (52 weeks, Week 1, 4, 12, 24, and 52)
 
Participants who meet the eligibility criteria will be randomized (ratio 1:1) using clinical site as a randomization variable to receive a loading dose of either tafenoquine 200 mg (2 x 100 mg tablets) or placebo daily for three consecutive days, followed by study treatment (tafenoquine 200 mg or placebo) once per week for 51 weeks, with safety follow-up visits at Weeks 4, 12, 24, and 52. A Columbia Suicidality Rating Scale (C-SSRS) Interview will be conducted at the Day 1 visit and every 4 weeks \pm 1 week thereafter. All efforts will be made to retain participants through to study completion. Reasons for withdrawal may include 1) withdrawal of consent, 2) lost to follow-up, 3) evidence of substance abuse that may affect the participant's capacity to complete the study in the investigator's opinion and 4) development of a new or worsening psychiatric disease (including suicidal ideation) at a non-scheduled visit or during routine M.I.N.I. evaluation that would jeopardize the safety of the participant if they continued in the study (see Section 9.2.7). If a participant stops taking their study drug, they should still continue to have all follow-up safety visits. If the subject wants to withdraw, they should have an end of study (EOS) visit (preferably 65-75 days after cessation of study treatment). The reasons for any treatment discontinuation (temporarily or permanently) will be documented on the electronic Case Report Form (eCRF).
 
Part 2 – Follow-up Phase (Week 64)
 
Due to the long t_{1/2} of tafenoquine (13-15 days with an expected 65-75-day washout period), all participants will return to the clinic at Week 64 for their EOS visits. If the participant has an ongoing AE, they will continue in Part 3 of the study, otherwise this is the final visit.
 
Part 3 – Follow-up Phase (Weeks 76, 89, and 104).
 
Participants who meet the criteria for continuation for additional safety assessments at the Week 64 visit will continue to be assessed for up to 3 more times at approximately 12-week intervals or until resolution or stabilization of the AE whichever is earlier.

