	
Orlando system).
 
 • After pupil dilation: 
 ○ MAIA microperimetry; ○ Heidelberg Spectralis SD-OCT (including wide field macula scan); ○ Heidelberg Spectralis qFAF (set of 3 images to ensure consistency in measurement); ○ Digital photograph of corneal surface (conventional and wide field); ○ Digital photograph of retina (conventional and wide field); ○ Slit lamp retinal examination and IOP measurement; and • Psychiatric Assessments: 
 ○ M.I.N.I. English Version 7.0.2 at Weeks 12, 24 and 52; ○ DHI (only collected if participant reports AE of dizziness or vertigo); ○ LSEQ; and, ○ C-SSRS – every 4 weeks \pm 1 week after the Week 52 Visit • AEs. 
Part 3 - Follow-up Ongoing AEs Weeks 76, 89, and 104 (Visits 8, 9 and 10) every 3 months until resolution (out to 12 months post final study drug dose – visits will only be scheduled if an AE was ongoing at a prior visit):
 
 • 12-lead ECG • Blood sampling. 
 • CBC and biochemistry; and • MetHb%. • Urinalysis (specific gravity, pH, glucose, protein, blood, ketones, leukocyte esterase, and nitrites). Microscopic examination (if blood, leukocyte esterase or nitrites are positive). • Ophthalmic assessments, including selected ophthalmic examination, microperimetry, BCVA (EDTRS), FM-100 hue testing, Mars letter contrast sensitivity test, M-chart and qFAF to follow only specific, abnormal results. • Psychiatric assessments: 
 ○ M.I.N.I. English Version 7.0.2. (If required to follow-up an AE or disorder). ○ DHI (if AE reported by participant); and • Any other AE. 
For compliance confirmation during the dosage phase – plasma samples will be taken at Weeks 1, 4, 12, 24, and 52. There is no specific timing for obtaining the pharmacokinetic (PK) sample during each scheduled visit. The date and time of the PK sample is to be recorded in the eCRF. Date, time, and number of tablets recorded in participant diary cards and/or electronic compliance management system will also be transferred to the eCRF.
 
Drawing of blood samples is estimated to be 135 mL/participant within the trial prescribed procedures and will not exceed 275 mL for the entire study period (Appendix 3).

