5. STUDY DESIGN

5.1. Overview

This randomized, double-blind, placebo controlled study will involve 600 healthy (G6PD normal) volunteers and will run in three parts. The Study Site may stagger enrollment of participants into weekly groups to accommodate the screening period.

Part 1 – Treatment phase (52 weeks)

Participants who meet the eligibility criteria will be randomized (ratio 1:1) using clinical site as a randomization variable to receive a loading dose of either tafenoquine 200 mg (2 x 100 mg tablets) or placebo daily for 3 consecutive days starting at Day 1, Week 1 (Visit 2), followed by study treatment (tafenoquine 200 mg or placebo) once per week for 51 weeks with safety follow-up visits at Weeks 4, 12, 24 and 52 (Visits 3, 4, 5, and 6). All efforts will be made to retain participants through to study completion. The reasons for withdrawal may include: 1) withdrawal of consent, 2) lost to follow-up, 3) evidence of substance abuse that may affect the participant's capacity to complete the study in the investigator's opinion, and 4) development of a new or worsening psychiatric disease (including suicidal ideation) at a non-scheduled visit or during routine M.I.N.I. evaluation that would jeopardize the safety of the participant if they continued in the study (see [Section 9.2.7](#)). If a participant stops taking their study drug, they should continue to have all follow-up safety visits. If the subject wants to withdraw, they should have an EOS visit (preferably 65-75 days after cessation of study treatment that includes all of the Week 64 assessments). The reasons for any treatment discontinuation (temporarily or permanently) will be documented on the eCRF.

Part 2 – Follow-up phase (12 weeks)

Due to the long t_{1/2} of tafenoquine (13-15 days with an expected 65-75-day washout period), all participants will return to the clinic at the Week 64 (Visit 7a and 7b) for their EOS visit. If the participant has an ongoing AE, they will continue in Part 3 of the study, otherwise this is the final visit.

Part 3 – Follow-up Phase (every 12 weeks, up to 12 months)

Participants who meet the criteria for continuation for additional safety assessments at Week 64 (Visit 7a and 7b) will continue to be assessed for up to 3 more times at approximately 12-week intervals or until resolution or stabilization of the AE whichever is earlier.

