The duration of subject's participation in the study will be up to 110 weeks, including a screening period of up to 6 weeks, a 52-week dosing period, and a 12-week follow-up period. If abnormalities are detected at the 12-week follow-up visit (Week 64 EOS) the subject will continue quarterly follow-up out to 12 months post last dose of IMP. For example, if corneal deposit was the only abnormality found during Week 64, then there is no need to repeat any of the ocular examinations except for corneal photography and corneal slit lamp examination at Weeks 76, 89 or 104 (Visits 8, 9 or 10).

The study will consist of the following for each participant:

- A screening period of up to 6 weeks prior to the first IMP dose. At the first screening visit (Visit 1a), subjects will be screened for eligibility with the exception of the

ophthalmologic assessments. If still eligible after the first visit, the subject will be scheduled for screening and baseline ophthalmic testing (Visit 1b).

- Randomization to receive tafenoquine or placebo in a 1:1 ratio using clinical site as a randomization variable;
- One 200 mg dose of tafenoquine per day for three consecutive days (loading doses; Days 1, 2 and 3) (Week 1, Visit 2) or equivalent dose of matched placebo;
- Once weekly 200 mg doses of tafenoquine or equivalent placebo on Week 2 through Week 52; Follow-up visits on Weeks 4, 12, 24, 52 and 64, and if applicable, Weeks 76, 89, and 104 to follow any ongoing AEs from the prior visit.

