10.11.2. Assessment and Recording of Adverse Events

It is the investigator's responsibility to document and report all AEs occurring in the clinical trial whether spontaneously reported by the participant, observed by the investigator (either directly or by laboratory or other assessments), or elicited by general questioning.

The period of observation for collection of AEs extends from the time of dosing (Day 1, Week 1 [Visit 2]) through the Week 64 follow-up visit. Those participants meeting the criteria for additional safety follow-up ([Section 8.5](#)) will be followed every 3 months thereafter to a maximum of 12 months until the AE resolves or stabilizes.

SAEs will be reported from the time of screening until 30 days following the EOS visit (Week 64) (if spontaneously reported by the participant). Serious adverse events experienced

after this 30-day period will only be reported if the investigator suspects a causal relationship with the study drug.

The following information should be recorded for all AEs:

- The name of the AE;
- The dates of onset and resolution of the event;
- The characteristics of the event (seriousness, intensity);
- The action taken in response to the event (including treatment required);
- The outcome of the event; and
- The relationship of the event to the study drug (causality assessment) and/or to study participation.

Standard toxicity grading

The medical assessment of AE severity of the study will be recorded in accordance with the Common Terminology Criteria for Adverse Events v 4.03 that went into effect June 14, 2010 ([CTCAE V4.03](#)). Note however, if the local site's normal blood pressure ranges overlap with that considered to be a grade 1 toxicity according to the CTCAE, that the upper limit of the local sites scale will be considered the cutoff for reporting an AE.

- Grade 1: Mild - asymptomatic or mild symptoms; clinical or diagnostic observations only; intervention not indicated;
- Grade 2: Moderate - minimal, local or non-invasive intervention indicated; limiting age-appropriate instrumental activities of daily living (ADL);
- Grade 3: Severe or medically significant but not immediately life-threatening; hospitalization or prolongation of hospitalization indicated; disabling; limiting self-care ADL;
- Grade 4: Life-threatening consequences; urgent intervention indicated.

Severity grading (AEs not included within [CTCAE V4.03](#))

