12.2.3.2. Secondary Endpoints

The incidence of AEs, SAEs, laboratory parameters and vital signs will be summarized descriptively by treatment group and study visit. The AEs will be summarized at $\geq 1\%$ (common) and $\geq 10\%$ (very common) level.

For the secondary safety endpoints, the proportion of participants with an abnormal change or new abnormal change will be compared by a Fisher's exact test between tafenoquine and placebo. The 95% CI of the abnormality rate will be summarized by Clopper Pearson Exact methodology. A logistic regression will be used to compare the risk of having the abnormality (odds ratio and 95% CI) between tafenoquine and placebo. These analysis methods will be applied to the following secondary safety endpoints: proportion of participants with abnormal changes from baseline observed on qFAF, proportion of participants with corneal deposits from slit lamp examination of the corneal epithelium, proportion of participants with new abnormal changes from baseline observed with color retinal digital photography (conventional and wide field), proportion of participants with new abnormal changes from baseline observed with microperimetry, proportion of participants with any new anomaly on the backlit ETDRS chart, proportion of participants with any clinically significant change in ETDRS BCVA (defined as ≥ 15 letter change [≥ 3 lines] of change in ETDRS BCVA at 4 meters), proportion of participants who develop a new color deficiency using the FM-100 hue test, proportion of participants who develop a loss of 0.12 or greater logCS on the Mars letter contrast sensitivity test, proportion of participants who develop a new identified psychiatric disorder, and proportion of participants with an AE of dizziness or vertigo and severity as assessed by the DHI.

For time to event safety endpoint, a log-rank test will be used to compare the time to onset/resolution of the event between tafenoquine and placebo. Cox regression will be used to compare the risk of having the safety endpoint (hazard ratio and 95% CI) between tafenoquine and placebo. The survival analysis methods will be applied to the endpoints of time to onset, and time to resolution of corneal deposits after treatment cessation.

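### The protocol gives two conflicting rules for when a participant with persisting corneal deposits leaves Part 3; if the stabilization exit is the one applied, the time-to-resolution analysis would overstate resolution

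*Combined protocol and SAP*

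**What the plan says.** **Follow-up may end at stabilization.** Section 5.1 (Part 3) provides up to three more assessments about 12 weeks apart, or "until resolution or stabilization of the AE whichever is earlier". The Synopsis (Study Design, Part 3) repeats this. Section 10.11.2 says participants needing more safety follow-up "will be followed every 3 months thereafter to a maximum of 12 months until the AE resolves or stabilizes", and its paragraph on outcome uses the same end point. I found no definition of stabilization. An abnormal slit-lamp examination is one of the Section 8.5 criteria for entering Part 3, so a participant with a deposit at Week 64 is covered by the Section 5.1 sentence.

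**Follow-up continues to resolution or 12 months.** Further on in Section 5.1, if abnormalities are found at Week 64, "the subject will continue quarterly follow-up out to 12 months post last dose of IMP". The example given is a participant whose only abnormality is a corneal deposit, who is spared repeat eye tests "except for corneal photography and corneal slit lamp examination at Weeks 76, 89 or 104 (Visits 8, 9 or 10". Section 9.2.6 likewise sets Week 76 and then quarterly examinations to 12 months. The Synopsis list of Part 3 assessments has visits "every 3 months until resolution (out to 12 months post final study drug dose", and its Study duration row also runs to AE resolution with a 12-month cap. None of these passages has a stabilization exit.

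**Analysis.** Section 12.2.3.2 applies log-rank and Cox methods to time to onset and "time to resolution of corneal deposits after treatment cessation". It gives no censoring date for an unresolved deposit. Section 12.2.1 says missing data are generally not imputed and leaves detail to a SAP to be finalized before unblinding.

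**The concern.** Log-rank and Cox methods treat a censored participant as having the same later chance of resolution as those still under observation. Someone who leaves because the deposit has stopped changing does not meet that assumption: the reason for leaving is itself a sign of non-resolution. The risk set is then enriched with improvers, and estimated resolution rises.

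The stabilization exit is a plausible site decision. Section 7.7 describes the deposits as benign and without visual consequence. Section 2.1.1.2 reports that ongoing mild retinal findings in Study 058 were not followed further.

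The exits could also fall unevenly by arm. In Study 057 (Section 2.1.1.1) all four placebo cases of new deposits resolved within 6 weeks of onset. In Study 033, 27 of 69 tafenoquine cases were still present at 3 months.

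What is at stake is the statement in Sections 2.3.2 and 5.5.1.2 that deposits reverse fully within a year. The Study 033 and Study 057 data behind it come from 6 months of dosing. This trial doses for 12 months, and time to resolution is where greater persistence would show.

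**Working it through.** **1. Source figures (Section 2.1.1.1, Study 033).** 69/74 = 93.2% with deposits, as stated there. Resolved at 3 months: 42/69 = 60.9%. Still present: 69 − 42 = 27, and 27/69 = 39.1%. All 27 resolved within 1 year. The plan states no event count or power for time to resolution, so there is no design figure to reproduce.

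**2. Time scale.** Dosing ends at Week 52. Weeks 64, 76, 89 and 104 are therefore 12, 24, 37 and 52 weeks after treatment ends.

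**3. Set-up.** Start with 69 cases: 42 resolve by Week 64 and 27 enter Part 3. Assume that *s* of the 27 never resolve and that the other 27 − *s* resolve in equal thirds at Weeks 76, 89 and 104. Estimated resolution is 1 − Π(1 − resolved/at risk). The plan does not name Kaplan-Meier. I use it as the descriptive counterpart of log-rank and Cox, with the same censoring assumption.

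**4. Three follow-up patterns.** Let R = 27 − (27 − *s*)/3, the number unresolved after the Week 76 examination.

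- *Everyone followed to Week 104:* unresolved = *s*/69, which is the true value.
- *All persistent cases leave as stable at Week 64 or Week 76:* everyone left at risk has resolved by Week 104, so the last factor is 0 and estimated resolution is 100%.
- *Half leave at Week 76 and half stay:* unresolved = (R/69) × (*s*/2)/(R − *s*/2).

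For *s* = 7, (27 − 7)/3 = 6.667 and R = 20.333.

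- Full follow-up: 1 − 7/69 = 89.9%.
- All leave at Week 76: 27 − 6.667 − 7 = 13.333 at risk at Week 89 and 6.667 at Week 104, all of whom resolve. The estimate is 100%, too high by 7/69 = 10.1 points.
- Half leave: 1 − (20.333/69)(3.5/16.833) = 1 − 0.0613 = 93.9%, too high by 4.0 points.

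**5. Range (52-week resolution; differences from unrounded values).**

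| Never resolve, of 27 | Followed to Week 104 (true) | All persistent cases leave as stable | Half leave at Week 76 | Overstatement: all / half |
|---|---|---|---|---|
| 0 | 100% | 100% | 100% | 0 / 0 |
| 3 | 95.7% | 100% | 97.6% | 4.3 / 2.0 |
| 7 | 89.9% | 100% | 93.9% | 10.1 / 4.0 |
| 14 | 79.7% | 100% | 85.3% | 20.3 / 5.6 |

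The second column is what the 12-month rule in Sections 5.1 and 9.2.6 would deliver. The third and fourth are what the stabilization exit could deliver.

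**The case against.** The strongest reply is that the stabilization wording is a general rule about AEs, while the passages specific to eye findings say the opposite and, in Section 5.1, name corneal deposits. In addition, the outcome list in Section 10.11.2 codes an unresolved, unchanged AE as Ongoing, and the Synopsis schedules the next visit when an AE was ongoing at the one before. On that reading an unchanged deposit recorded as an AE stays in follow-up and the bias is zero. This stands. A reader might infer that persistent deposits do leave early and that the analysis censors exactly the cases that fail to resolve. The documents support neither as fact: early exit is one of two readings, and censoring at exit is inferred from the methods named.

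Three further points also stand.

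- Section 5.6 uses stabilization wording too, but only for laboratory values, so it is not evidence here.
- The data quoted give no support for a large persistent fraction. All Study 033 cases resolved within a year, and the last Study 057 case by Week 48. Study 057 incidence should not be combined with Study 033 persistence to forecast Part 3 entrants, because all but one of Study 057's 15 new tafenoquine cases resolved within 12 weeks of onset.
- Unresolved cases would not vanish from the report, since Section 12.2.3.2 also asks for tabulation and a listing.

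The reply does not remove the conflict. Nothing says which rule prevails, stabilization is left to judgment, and the two rules sit in one section and reach the same participant.

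**Conclusion.** The contradiction in exit rules is established by the text. The bias is conditional: absent if the 12-month rule governs, and towards overstated resolution if the stabilization exit is applied to deposits. If all persistent cases leave as stable, the overstatement equals the persistent share of all deposit cases: 4.3 points for 3 of the 27, 20.3 points for 14. If half leave at Week 76, it is about 2 to 6 points over the same range. With no persistent cases, as in Study 033 at 1 year, it is zero. These sizes rest on an assumed number of persistent cases, even resolution among the rest, and censoring at exit.

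It does not follow that the censored analysis should be replaced by one counting every stable exit as unresolved. Suppose, per 100 entrants, that 25 leave as stable, 5 of those later resolve, and 5 others remain unresolved. Counting all stable exits as unresolved gives 25 + 5 = 30% against a true 20 + 5 = 25%. That approach errs the other way and belongs in a sensitivity analysis.

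The point concerns a secondary endpoint and leaves the primary comparison untouched. It is worth correcting because the endpoint bears directly on reversibility after longer dosing.

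**What to change.** 1. Reconcile the Synopsis (Study Design, Study duration and Part 3 assessments) and Sections 5.1, 9.2.6 and 10.11.2, so that one exit rule applies to corneal deposits in both arms and at all sites. If stabilization remains a reason to stop, define it. Which rule to keep is for the sponsor and investigators; the analysis needs only one.
2. Record the reason for leaving Part 3 in the eCRF.
3. In Section 12.2.3.2 and the SAP, state the censoring date for an unresolved deposit: the last slit-lamp examination, Week 104 at the latest.
4. Report by arm the numbers resolved, stable-unresolved and lost at the last examination.
5. Keep the log-rank and Cox analysis, and add a sensitivity analysis in which stable-unresolved exits count as unresolved through Week 104.

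The cost is one eCRF field and a small amount of extra analysis. If follow-up to 12 months is the rule kept, Week 89 and Week 104 slit-lamp visits already in the schedule must also be completed.

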5.2. Study Endpoints

5.2.1. Primary Endpoint

Proportion of subjects with protocol-defined SOSE. SOSE is assessed by significant retinal changes from baseline using SD-OCT and qFAF. The details of significant protocol defined retinal changes using SD-OCT and qFAF are defined in [Table 5](#).

5.2.2. Secondary Endpoints

- The incidence, severity and relationship to the IMP of AEs (including unexpected toxicities, AEs encountered during or after IMP administration), safety laboratory parameters, vital signs, and ECG up to and including the end of treatment period Week 52 (Visit 6).
- Mean change from baseline in key SD-OCT parameters including CST, TMV, parafoveal (inner ring of ETDRS grid) retinal thickness and the proportion of participants ellipsoid and interdigitating zone disruption (as per [Table 5](#)).
- Proportion of participants with abnormal changes from baseline observed on qFAF using the Spectralis HRA+OCT device with grey scale values extracted from these images for statistical analysis using qFAF software (Heidelberg Engineering).
- Mean change from baseline in BCVA.
- Proportion of participants with corneal deposits from slit lamp examination of the corneal epithelium.
- Time to onset of corneal deposits and overall time duration to resolution post treatment start.
- Time duration to resolution of corneal deposits after treatment cessation.
- Proportion of participants with new abnormalities compared with baseline observed with color retinal digital photography (conventional and wide field).
- Proportion of participants with new abnormalities compared with baseline observed with microperimetry.
- Proportion of participants with any new anomaly on the backlit ETDRS chart.
- Proportion of participants with any clinically significant change in ETDRS BCVA (defined as ≥ 15 letter change [≥ 3 lines] of change in ETDRS BCVA at 4 meters)
- Proportion of participants who develop a color deficiency using the FM-100 hue test.
- Proportion of participants who develop a loss of 0.12 or greater logCS on the Mars letter contrast sensitivity test.

- Proportion of participants who develop a psychiatric disorder in accordance with the DSM-5 as assessed with the M.I.N.I. 7.0.2 assessment questionnaire and suicidal ideation or suicide attempt by C-SSRS interview.
- Proportion of participants with an AE of dizziness or vertigo and severity as assessed by the DHI.
- Mean change from baseline in GTS, QOS, AFS, and BFW as assessed by the LSEQ.

